7.3 Screening/Baseline Testing/Prestudy Evaluation

Following informed consent, participants will be pre-registered to the study.

Participants in the surgical cohort will undergo a screening evaluation including blood chemistry (HBV, HCV, INR, Total bilirubin, ALT, AST, Alkaline phosphatase, BUN, creatinine, Creatine phosphokinase, Calcium, Total protein, Albumin, quantitative HCV RNA [if HCV+]), and hematology (CBC with 5-part differential, platelets). Blood will also be drawn for baseline levels for translational endpoints. Participants will undergo a history and physical, review of baseline symptoms, and review of concomitant medications. He/she will then undergo a percutaneous or transjugular liver biopsy of non-tumor-bearing liver to obtain study tissue for baseline analyses.

Participants in the non-surgical cohort will provide consent to obtain specimens from previous (≤ 3 months prior to pre-registration) clinical liver biopsy. Formalin-fixed specimens will be submitted to Mayo Clinic Pathology Research Core (PRC) for phospho-EGFR assessment. If the assessment is negative (< 100 stained pixels), the participant will be considered a screen failure and will not continue on-study. If the assessment is positive (≥ 100 stained pixels), participants will undergo additional screening evaluation including blood chemistry (HBV, HCV, INR, Total bilirubin, ALT, AST, Alkaline phosphatase, BUN, creatinine, Creatine phosphokinase, Calcium, Total protein, Albumin, quantitative HCV RNA [only if HCV+]), and hematology (CBC with 5-part differential, platelets). Blood will also be drawn for baseline levels for translational endpoints. Participants will undergo a history and physical, review of baseline symptoms, and review of concomitant medications.

If the participant meets all of the eligibility requirements, he/she will be registered to the study and assigned to a dose group.

7.4 Evaluation During Study Intervention

7.4.1 Study Intervention

Once the date of liver resection surgery (surgical cohort) or liver biopsy (non-surgical cohort) has been established, participants will receive a daily dose of erlotinib starting 6 days prior to the scheduled surgery/biopsy, including a 7th dose on the morning of surgery/biopsy according to the dose level assigned at the time of registration. Intervention of 7 days is ideal, but participants receiving daily erlotinib for 5-14 days will be considered evaluable for endpoint assessment as long as they have taken 85% of scheduled doses and receive their final dose on the day of surgery/biopsy before the procedure.

Participants will be contacted by telephone on Day 3 (+/- 1 day) and Day 6 (+/- 1 day) for adverse event assessment, review of concomitant medications, and review of schedule of events for Days 3, 6 and 7. These assessments are required.

On days 1, 2, 4, 5, and all others that do not have scheduled study visits, the study team will attempt to contact the participant by telephone, text message, or email (per the participant's stated preference) to remind them to take their study medications. Voice mail messages may be left if allowed per institutional guidelines. These attempts will be documented in source documentation. It will not be considered a deviation if contact is not made.

Participants whose surgeries/biopsies are rescheduled and will take erlotinib for 10 to 14 days will be contacted one additional time between Day 6 and the day of surgery/biopsy for adverse event assessment, review of concomitant medications, and review of scheduled events.

7.4.2 Definition of Dose Limiting Toxicities (DLTs)

For adverse events deemed at least possibly related to study agent:

Toxicity	Definition
Rash	≥ Grade 4
All other AEs deemed at least possibly related to study agent	≥ Grade 3

Toxicities are based on the National Cancer Institute (NCI) Common Terminology Criteria for Adverse Events (CTCAE) version 4. All events that are deemed Serious Adverse Events will be reported within 24 hours of learning of the occurrence (See Section 11.2 for details).

Number of Participants with DLT at a Given Dose Level	Escalation Decision Rule
0 or 1 out of 5	Declare the dose level safe and follow the rules for determining minimum effective dose (MED).
2 or 3 out of 5	Enter 5 new participants at this dose level: 
 If, among all enrolled participants at this dose, the incidence of DLT is less than 33%, then declare the dose level safe and follow the rules for determining MED. If, among all enrolled participants at this dose, the incidence of DLT is ≥ 33% then this dose is declared to be above the maximum tolerated dose (MTD) and the dose escalation is stopped, regardless of phospho-EGFR staining response. Declare the next lower dose the MTD if ≥ 5 participants have already been treated at that dose.
4 or 5 out of 5	Declare this dose to be above the MTD and de-escalate without further enrollment at this dose level.
If no DLTs are seen at any of the dose levels, then the MTD will be the maximum delivered dose. MTD will be defined as the highest safely administered dose at which < 33% of participants experience DLT OR no DLT is observed out of 5 participants at the maximum dose level, provided no DLT is observed at any of the previous dose levels.	

Evaluation of toxicity will occur at each participant contact point. All DLTs qualify as Serious Adverse Events and will be reported to the medical monitor within 24 hours (See Section 11.2). If a suspension in enrollment to evaluate toxicity is required, the medical monitor will contact the CPN Operations Office, who will communicate that information immediately to the CPN Registration Office and all participating organizations.

7.4.3 Dose Escalation/De-escalation

Enrollment will be temporarily suspended after every 5 participants to evaluate phospho-EGFR response. If all 5 participants are evaluable, the dose level has been deemed safe, and phospho-EGFR is inhibited (i.e., a response, see Section 13) in at least 40% of evaluable participants, then enrollment will

continue at the next lower dose. If there are < 5 evaluable based on phospho-EGFR staining and the DLTs are below the limits specified above, then 5 more will be enrolled at that dose level in an attempt to reach a total of at least 5 evaluable participants. If the total number of evaluable participants remains < 5 and the dose level is deemed safe, then 5 more participants will be enrolled at this same dose level.

At dose level 0, if fewer than 2 responses are observed (in the first 5 evaluable participants) and the dose level is deemed to be safe, 15 participants will be enrolled at the next higher dose level (+1). If at least 2 participants have a response in the first 5 evaluable at this dose level and the dose level is deemed to be safe, this dose level will be declared the MED and further study with this dose will be warranted. If fewer than 2 responses (in the first 5 evaluable) are observed at this dose level, 15 participants will be enrolled at the next higher dose level (+2). If at least 2 responses are observed (in the first 5 evaluable participants) at this dose level and the dose level is deemed to be safe, this dose level will be declared the MED and further study with this dose will be warranted. If fewer than 2 responses are observed at this dose level (in the first 5 evaluable participants), we may consider including additional dose levels, after discussion with the DCP medical monitor, to find the MED for this study.

The lowest dose level at which there are ≥ 5 participants and $\geq 40\%$ of these evaluable participants demonstrate a phospho-EGFR response will be considered the minimum effective dose (MED).

Reopening to enrollment after a temporary closure will occur after consultation with the DCP medical monitor.

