13.4 Primary Objective, Endpoint(s), Analysis Plan

The primary objective of this study is to determine a safe and minimum effective dose (MED) of daily erlotinib that inhibits EGFR signaling in the target organ (liver) as assessed by phospho-EGFR staining.

We have no data to demonstrate that this will be different between the surgical and non-surgical cohorts, thus the primary endpoint will be analyzed overall, including data from both cohorts. The primary endpoint is to find the safe and MED that achieves a response rate of at least 40%, where a response is defined as an evaluable patient that achieves a 50% reduction in the percentage of positive pixels in the phospho-EGFR staining in the liver from baseline after a 7 day intervention period with daily erlotinib. See Section 13.6 for criteria for the evaluability of the primary endpoint.

Assuming a binomial distribution for the number of responses in 5 evaluable participants at a given dose level, and a true response rate of 60%, the probability of observing at least 2 responses is 91%. We felt this was adequate evidence of activity in a small pilot study (see table below with the details), given that a true response rate of 60% could not be ruled out even if we only observe a 40% response rate.

Number of responses (x)	P(x)
0	0.010
1	0.077
2	0.230
3	0.346
4	0.259
5	0.078

In summary, we will find the MED that achieves a 40% or higher observed response rate in participants that have at least some EGFR staining at baseline.

Once the MED is determined, we will expand accrual at that dose level to a total of 20 participants (to obtain 10 evaluable) to further evaluate the safety and response rate along with other translational endpoints at that dose level.

With 10 evaluable participants, we would be able to develop a 2-sided 90% confidence interval with a margin of error of about 25% for the response rate endpoint. Given that this is a pilot study, we would use the information we gain from the primary and secondary/translational endpoints to plan for a larger study that would further evaluate this treatment in this disease setting.

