13.8 Evaluation of Response

Minimal Effective Dose (MED) determination (using dose levels defined in section 5.1)

In addition to assessment of responses discussed below, the dose-escalation/de-escalation decision will also depend on safety, see Section 7.3.

Ten participants will be enrolled at the starting dose level (dose level 0) and if at least 2 in the first 5 evaluable participants have a response (40%) and the dose level is deemed to be safe, 10 participants will be enrolled at the next lower dose level (-1). If at least 2 participants have a response in the first 5 evaluable at this dose level and this dose level is deemed to be safe, 10 participants will be enrolled at the next lower dose level (-2). If at least 2 responses are observed at this dose level as well (in the first 5 evaluable) and this dose level is deemed to be safe, then this dose level will be considered the observed MED for this study, and further study will be warranted at this dose level.

At dose level 0, if fewer than 2 responses are observed (in the first 5 evaluable participants) and the dose level is deemed to be safe, 10 participants will be enrolled at the next higher dose level (+1). If at least 2 participants have a response in the first 5 evaluable at this dose level and the dose level is deemed to be safe, this dose level will be declared the MED and further study with this dose will be warranted. If fewer than 2 responses (in the first 5 evaluable) are observed at this dose level, 10 participants will be enrolled at the next higher dose level (+2). If at least 2 responses are observed (in the first 5 evaluable participants) at this dose level and the dose level is deemed to be safe, this dose

level will be declared the MED and further study with this dose will be warranted. If fewer than 2 responses are observed at this dose level (in the first 5 evaluable participants), we may consider including additional dose levels to find the MED for this study.

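### The MED has two response criteria that can disagree once more than 5 participants are evaluable, and no rule says how the expansion response data bear on it

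*Combined protocol and SAP*

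**What the plan says.** **First-5 criterion.** Section 7.4.3, for levels +1 and +2: "If at least 2 participants have a response in the first 5 evaluable at this dose level", and the level is deemed safe, "this dose level will be declared the MED and further study with this dose will be warranted". Section 13.8 repeats this. It applies the same count on the way down, and at level -2 the outcome is worded "then this dose level will be considered the observed MED for this study, and further study will be warranted at this dose level". At levels 0 and -1, meeting the count leads to the next lower level and not to a declaration.

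**Percentage criterion.** Section 7.4.3 then gives a general definition: the lowest level with at least 5 participants at which at least 40% "of these evaluable participants demonstrate a phospho-EGFR response will be considered the minimum effective dose (MED". Section 13.4 sums up in the same spirit: "In summary, we will find the MED that achieves a 40% or higher observed response rate". Neither sentence is confined to the first 5.

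**Expansion.** It opens once the MED is determined. Section 3 says it is meant to improve confidence in the observed response rate. Section 13.4 says it is "to further evaluate the safety and response rate along with other translational endpoints at that dose level", with a two-sided 90% confidence interval on 10 evaluable. Appendix E ends each successful path at enrolling the expansion. Its pooling steps combine adjacent dose stages, not the expansion with earlier participants.

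**Justification.** Section 13.4 takes "a true response rate of 60%, the probability of observing at least 2 responses is 91" per cent and adds that "a true response rate of 60% could not be ruled out even if we only observe a 40% response rate".

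**The concern.** The MED is the primary endpoint, and Section 2.3 expects the results to define the dose schedule for later randomized studies. The plan should therefore lead from one set of data to one answer on whether a dose met the 40% response criterion. With more than 5 evaluable at a level it may not: one sentence of 7.4.3 can name the dose while another does not.

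The expansion roughly doubles or triples the evaluable data at the chosen dose, yet no section gives it a threshold, says whether it is pooled with the first 5, or says what follows if the response rate falls below 40%. Following the first-5 rule literally could present a dose as meeting the primary response criterion when its complete data do not.

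The justification shows only how often a good dose passes. It gives no pass probability at any lower true rate.

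**Working it through.** **1. The plan's own figure.** For X ~ Binomial(5, p), P(X ≥ 2) = 1 − (1−p)^5 − 5p(1−p)^4. At p = 0.60 this is 1 − 0.0102 − 0.0768 = 0.913. The 91% reproduces, and so do all six entries of the table in 13.4.

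**2. Where the criteria part.** At exactly 5 evaluable, 2/5 = 40% and they coincide. Beyond that:
- 2/5 then one non-responder: 2/6 = 33%. Then two: 2/7 = 29%. First-5 met, percentage not met.
- 1/5 then two responders: 3/7 = 43%. First-5 not met, percentage met.

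**3. Is more than 5 evaluable likely?** Section 13.3 assumes 30 to 40% non-evaluable, so 10 enrolled give 10 × 0.60 = 6 to 10 × 0.70 = 7 evaluable. Section 7.4.3 pauses after 5 enrolled and can move on with exactly 5 only if all are evaluable: 0.60^5 = 8% to 0.70^5 = 17%, if participants are independent. At the 15 per escalated level stated in 7.4.3 (13.8 says 10), the expected number is 15 × 0.60 = 9 to 15 × 0.70 = 10.5.

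**4. After the expansion.** Section 13.3 plans 25 evaluable: 3 levels × 5, plus 10. That is 5 + 10 = 15 at the MED. Section 13.4 expands to a total of 20 enrolled to obtain 10 evaluable, which can also be read as 10 evaluable in all at that dose. I computed both.

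Probability of passing on the first 5 and also having at least 40% of all n evaluable:

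Σ over x = 2 to 5 of P(X = x) × P(Y ≥ k − x), with Y ~ Binomial(n − 5, p); k = 6 for n = 15 and k = 4 for n = 10.

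| True rate | First 5 only | Also ≥ 6/15 | Also ≥ 4/10 |
|---|---|---|---|
| 10% | 8.1% | 0.2% | 1.0% |
| 20% | 26.3% | 4.6% | 9.5% |
| 40% | 66.3% | 48.9% | 52.9% |
| 60% | 91.3% | 89.6% | 88.9% |

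Of doses passing on the first 5, the share that end below 40% of 15 is (26.3 − 4.6)/26.3 = 83% at a true 20%, (66.3 − 48.9)/66.3 = 26% at 40%, and (91.3 − 89.6)/91.3 = 2% at 60%.

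These are probabilities for one tested dose, given that it is reached and safe. The documents supply only the 60% rate; the others are assumed. Responses are taken as independent with a constant rate.

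**5. An extreme case.** 2/5 then 0/10 is 2/15 = 13%, exact (Clopper-Pearson) 90% CI 2% to 36%, wholly below 40%. The first-5 rule is still met. For 2/5 alone the exact 90% CI is 8% to 81%, so the result that does not rule out 60% does not rule out 10% either.

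**The case against.** A reader might infer that nothing found later can overturn a declared MED. The documents do not say so. That would be an argument from silence, and the percentage definition, applied to accumulated data, would itself overturn the call. Nor can it extend to safety: Sections 12.4 and 13.7.1 allow for suspending accrual on adverse events throughout.

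Other points on that side:
- The percentage definition does not say all evaluable participants and does not mention the expansion. It can be read as summarising the cohort-of-5 rule above it. That reading is possible, but the text does not settle it, and 13.4 is not limited to 5 either. The ambiguity stands as the finding.
- The probabilities might be taken as chances of naming the MED. They are not. On the way down, 75 mg becomes the expansion dose under Appendix E only if it passes and 50 mg is safe but not effective. With assumed true rates of 60% and 40%, that is 0.913 × (1 − 0.663) = 31%.
- The 13.4 argument might be called inverted. It is a one-sided screening rationale for a small pilot: incomplete, not backwards.
- A low expansion rate would be visible, because 13.4 plans a confidence interval. True, but an interval does not decide whether the criterion is reported as met. The 2/5-then-0/10 case is also rare: 10p²(1−p)^13 peaks at 2.8%, and is 0.2% at a true 40%. It illustrates the gap; it does not measure it.
- Fifteen evaluable at the MED is an assumption. Amendment 9 cut target accrual to 31 with study agent about to expire, so it may not be reached.

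**Conclusion.** The concern holds as an unreconciled definition plus a missing rule. Sections 7.4.3, 13.4 and 13.8 give two response criteria for the MED that can disagree in either direction above 5 evaluable, which the plan's own non-evaluable share makes likely. No section ties the expansion response data to the MED.

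The gap matters most for weakly active doses. At an assumed true 20%, a tested dose passes the first-5 rule 26% of the time, against 5% (15 evaluable) or 9.5% (10 evaluable) if the full data must also reach 40%. At the planned 60% the criteria barely differ: 91% against 89 to 90%. The conclusion is the same on either reading of the expansion size.

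It concerns response only. In a pilot that will report a confidence interval and feed a larger study, it should be corrected, but it does not invalidate the design.

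**What to change.** Reconcile Sections 3, 7.4.3, 13.4, 13.8 and Appendix E on which participants define the MED response criterion:

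- Call the first-5 result provisional; it opens the expansion as now.
- Base the final statement that a dose met the 40% response criterion on all evaluable participants at that dose, with an exact 90% CI. Show the expansion-only rate beside it, because the first 5 selected the dose.
- If the pooled rate is below 40%, report that the criterion was not met.
- State which definition governs when a level has more than 5 evaluable before any expansion, so that 1/5 followed by 2/2 is covered as well as 2/5 followed by 0/2. The provisional label alone does not settle that case.
- In 13.4, set pass probabilities at lower true rates beside the 91%.
- Reconcile the enrolment figures that fix the denominator: 10 or 15 per escalated level (13.8, 7.4.3), and an expansion of 15 or 20 (13.3; 3 and 13.4).

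The cost is wording, with no extra participants and no change to dosing or safety rules. The downside is statistical: a dose truly at 40% is confirmed about 49 to 53% of the time instead of 66%. At 60% it is 89 to 90% instead of 91%.

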7.5 Evaluation at Completion of Study Intervention

The participant will undergo a brief physical exam with vital signs. If institutional standards of care include a physical exam and this information is available to the study team, then the clinical physical exam will suffice. This evaluation may occur on the day prior to surgery/biopsy or prior to administration of anesthesia on the day of surgery/biopsy. Any remaining study agent supply and completed medication diary will be collected. The final assessment of adverse events and recording of concomitant medications will occur during this evaluation. Participants will be asked to complete the Was It Worth It (WIWI) questionnaire.

The final dose of erlotinib will be taken on the day of surgery/biopsy (prior to the procedure) with a sip of water. After the final erlotinib dose and prior to surgery/biopsy, repeat research blood draw and laboratory evaluations including blood chemistry (HBV, HCV, INR, Total bilirubin, ALT, AST, BUN, Creatinine, Alkaline phosphatase, Creatine phosphokinase, Calcium, Total protein, Albumin, quantitative HCV RNA [only if HCV+], and hematology (CBC with 5-part differential, platelets). Note that HBV and HCV do not have to be repeated at the post-intervention evaluation if the screening test results were negative/undetectable.

7.6 Post-intervention Follow-up Period

Immediately following the liver resection operation or liver biopsy, portions of liver from the resected specimen will be collected and processed for study (See Section 10 for details).

7.7 Methods for Clinical Procedures

7.7.1 Pre-intervention

After informed consent and screening, and prior to initiation of erlotinib treatment, all surgical cohort participants will undergo a percutaneous or transjugular biopsy of their cirrhotic/fibrotic liver in a non-tumor bearing area. Participants should remain NPO after midnight before the scheduled biopsy to allow for use of conscious sedation if indicated. Whether to perform the biopsy under local anesthesia or under conscious sedation will be at the discretion of the clinician performing the biopsy. For percutaneous biopsy a 16-gauge core is preferable; an 18-gauge core is acceptable. All participants will be monitored post-procedure according to institutional standards of good clinical practice, after which time they may be discharged to home. The biopsy may be conducted via transjugular approach or under ultrasound guidance as deemed appropriate and will consist of 4 samples, of which 2 will be placed in RNAlater (Qiagen), and two will be placed in formalin. All samples will be stored in a refrigerator. If the clinician performing a percutaneous biopsy is unable to obtain at least two (2) core biopsies safely (e.g. participant starts bleeding), the clinician should abort the attempt. The participant will be considered not evaluable.

After informed consent, specimens will be obtained from clinically-indicated liver biopsy for all non-surgical cohort participants. Formalin blocks or unstained slides will be obtained and submitted to the CPN Pathology Coordinator for accessioning. The Pathology Coordinator will submit them to Mayo Clinic Pathology Research Core (PRC) for phospho-EGFR assessment.

